Most hemodialysis patients receive therapy sessions thrice weekly, typically for 12 hours per week. The stability of sessions varies, with an average of 20% becoming unstable—most commonly from intradialytic hypotension (IDH); this affects half of all hemodialysis patients.⁴⁵⁻⁴⁸ IDH may prompt cramping, dizziness, vomiting, fainting, and fatigue.^{40, 49, 50} Serious unstable sessions lead to hospitalization or even death on days in which dialysis was received⁵¹⁻⁵³. The chief cause of unstable hemodialysis sessions is rapid removal of large volumes of fluid; this is driven by both patient-level and facility-level factors.⁴⁸ Indeed, there are wide facility-level variations in IDH rates after controlling for patient characteristics,⁴⁸ 20% of the variation in IDH is predicted at the patient level.⁵⁴

Hemodialysis session instability is associated with repetitive and cumulative cardiovascular and other organ system injury.⁵⁵⁻⁵⁷ Large volumes of fluid (3 liters or more) may be removed at higher than desired ultrafiltration rates during a typical HD session due in part to high interdialytic weight gains. In the face of pre-existing diminished cardiovascular reserves, this may result in HD instability and repeated myocardial hypoperfusion with resultant wall-motion abnormalities, an event called “myocardial stunning”.⁵⁵⁻⁵⁷ Emerging evidence shows it may be responsible for injury resulting from hypoperfusion in other microcirculatory beds, including in the central nervous system (e.g., repetitive neurological injury leading to cognitive dysfunction).⁵⁸

The most common form of hemodialysis session instability, IDH, predicts low quality of life, hospitalization and mortality.^{47, 59} Our team⁶⁰ and others^{17, 18} have shown that a care process directly linkable to IDH onset, the ultrafiltration rate (i.e. rate of fluid removal) greater than 10 ml/h/kg bodyweight, is linked to elevated mortality risk. Of note, the FMCNA UFR goal is <13 ml/kg/hr. We have also shown that the thrice-weekly schedule paradigm is associated with significantly higher mortality earlier in the week, potentially due to the long interdialytic interval over the weekend, which leads to a greater need for fluid removal early in the week.⁶¹ Negative symptoms may result in session shortening by patients or providers.⁶² A national survey found that 90% of hemodialysis providers had witnessed sessions stopped due to patient status in the three months prior.⁶³

2.1.4 IMPORTANCE OF THE STUDY:

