3.2 STUDY OUTCOME MEASURES

3.2.1 Primary Outcome Measures

Dialysis session stability (primary outcome, Aim 1).

We define a dialysis session as unstable based on direct blood pressure measures that are routinely gathered during hemodialysis care. Secondary measures of the primary outcome include: (1) additional direct blood pressure measures; and (2) hospitalization or death on day in which dialysis was received.

Primary measure. The primary indicator of IDH based on direct blood measures after session start will be sitting Systolic blood pressure (SBP) falling below 100 mmHg (using lowest SBP during session) if starting SBP ≥ 100 .

Secondary measures of primary outcome. Secondary measures of IDH based on direct blood pressure measures will include: the lowest (minimum) valid SBP below 100 mmHg during the session if starting SBP is ≥ 100 , the number of SBP measurements < 100 mmHg (using raw blood pressure measures, time of blood pressure measure, and starting SBP) if starting SBP is ≥ 100 , and whether the sitting SBP falls below 90 mmHg (using lowest SBP during session) if starting SBP ≥ 100 .

Hospitalization or death on a day in which dialysis was received will be determined based on matching the date of cardiovascular or fluid-related hospitalization or death with the date/time of the administered dialysis session, and assessing the hospital discharge diagnosis or primary cause of death based on FMCNA records.

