Mediation Analyses. The second part of these analyses aim to identify mechanisms of action for the interventions, such as changes in patient or practitioner behavior and session characteristics; these changes in behavior will identify important pathways for improvement in reducing IDH. However, these analyses are not intended to be used for causal inferences. The basic mediation analysis involves 3 steps: (1) confirm that the intervention predicts the outcome (and if not, then mediation analysis is not relevant), (2) confirm that the intervention predicts the mediator (i.e., that the intervention has resulted in specific changes in patient or practitioner behavior; if not, then the potential mediator cannot mediate an intervention effect), and (3) in a model predicting the outcome with covariates including both the intervention and the mediator, confirm that the intervention effect has been reduced after adding the mediator to the model, and confirm that the mediator is a statistically significant predictor of the outcome. The role of moderation in a mediation analysis can also be tested. Each potential mediator is tested

separately, without adjusting for other mediators, although associations between mediators can separately be assessed for improved interpretation.

Mediators of the Primary Outcome: The following variables will be examined as potential mediators of the treatment effect on the primary outcome of dialysis session stability:

Patient-level variables: (1) patient session instability prevention behavior; (2) fluid management practice patterns; (3) number and categories of BP medications patient is taking; (4) fluid adherence (inter-dialytic weight gain); (5) dialysis adherence; (6) patient symptoms (symptom burden measure and recovery time); (7) hospitalizations for cardiovascular or fluid-related causes; and (8) quality of life.

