Session-level variables to be assessed for potential mediation effects include: (1) treatment time delivered; (2) average session UFR; (3) cooled dialysate used; (4) sodium modeling used; (5) ultrafiltration modeling used; (6) ultrafiltration variability for whole session, or up until incident of IDH (if IDH occurs) (difference between the highest and lowest UFR, standard deviation of the UFR measures, the square root of the mean squared differences of successive UFR measures); (7) sitting-to-standing difference in SBP (orthostasis at beginning of session); (8) starting SBP; (9) slope of changes in SBP over 30 minute intervals for whole session, or up until incident of IDH (if IDH occurs); (10) values and times of lowest and highest SBP readings as a measure of range of SBP during the dialysis session; (11) patient request re: fluid removal at this session; (12) fluid adherence (inter-dialytic weight gain) at this session; (13) previous achievement of post-dialysis target weight; and (14) previous session instability.

Sensitivity Analyses. In addition to the sensitivity analyses described above, we will examine the effect that patient compliance/non-compliance rates, i.e., percent of patients who accept peer mentoring and checklist adherence for provider intervention, have on the results. The sensitivity analyses aim to assess the robustness of the conclusions based on the analyses of the primary outcome – specifically to determine whether the findings hold under different methods of defining the primary outcome. Thus we will conduct sensitivity analyses for the secondary measures of session instability described above. As part of this, because we will know the dates and causes of hospitalization and death by cardiovascular- or fluid-related causes, we will identify those events that took place on days in which dialysis was administered. Accordingly, we will conduct a sensitivity analysis of the primary outcome of dialysis session stability both with, and without, those events on dialysis days included. For the primary outcome analyses, we will also conduct a sensitivity analysis without the sessions of patients who begin that session with a sitting pre-dialysis SBP of 100-110 MmHg and whether the sitting SBP falls below 90 mmHg (using lowest SBP during session) if starting SBP ≥ 100 .

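### Lowest in-session SBP is listed as a mediator of IDH, the outcome it defines, and no time-order rule keeps consequences of IDH off the mediator list

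*Combined protocol and SAP*

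**What the plan says.** Section 3.2.1 bases the primary indicator of IDH on "sitting Systolic blood pressure (SBP) falling below 100 mmHg (using lowest SBP during session", given a starting SBP of at least 100. The same section lists the session's minimum SBP as a secondary measure of the primary outcome. It also lists cardiovascular or fluid-related hospitalization on a dialysis day.

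Section 11.4 (Aim 1, Mediation Analyses) sets out three steps. Step 1: the intervention must affect the outcome, otherwise the analysis stops. Step 2: the intervention must affect the candidate mediator. Step 3: with both in the model, the intervention effect must shrink and the mediator must be significant. Mediators are tested one at a time, and the section says the results are not for causal inference.

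The session-level list for the primary outcome contains item "10) values and times of lowest and highest SBP readings as a measure of range of SBP during the dialysis session" and item (9), "slope of changes in SBP over 30 minute intervals for whole session, or up until incident of IDH (if IDH occurs". The patient-level list ends with items "6) patient symptoms (symptom burden measure and recovery time); (7) hospitalizations for cardiovascular or fluid-related causes; and (8) quality of life".

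Section 2.1.3 gives the direction the protocol has in mind: "IDH may prompt cramping, dizziness, vomiting, fainting, and fatigue", and IDH "predicts low quality of life, hospitalization and mortality". The Aim 2 mediator list in Section 11.4 makes IDH itself, as item (14), a candidate mediator of the secondary outcomes.

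**The concern.** A mediator has to be a step between the intervention and the outcome. The lowest SBP of a session is not a step towards IDH as defined here; it is IDH on its continuous scale. Anything that lowers the IDH rate raises the nadir, so steps 2 and 3 add almost no information once step 1 has passed. Items (6) and (9) of the session-level list offer a version truncated at the event, and items (13) and (14) refer to previous sessions. Item (10) has neither safeguard.

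The patient-level items raise a weaker form of the same problem. A consequence of IDH is correlated with IDH and, if the intervention works, with the intervention. The three steps contain no time-order condition, so they cannot tell a cause of IDH from a result of it. At stake is the explanation of any effect: Section 11.1 relies on mediation and moderation to explore why one intervention might do better than the other.

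**Working it through.** **Step A: the texts side by side.**
- Outcome (Section 3.2.1): unstable if lowest SBP < 100, among sessions starting at 100 or above. Mediator (Section 11.4, item 10): value of the lowest SBP. Within eligible sessions, P(unstable | lowest SBP < 100) = 1 and P(unstable | lowest SBP ≥ 100) = 0.
- Symptoms, hospitalization and quality of life are consequences of IDH in Section 2.1.3, mediators of IDH in the Aim 1 list, and outcomes mediated by IDH in the Aim 2 list. The two lists are circular.
- Section 3.2.2 accepts the earliest KDQOL survey within 12 months after intervention start. Follow-up is 24 + 12 = 36 weeks, so the survey can come after the sessions it would mediate.
- Hospitalization carries a window (the past 4 weeks) in the Aim 2 list and none in the Aim 1 list.

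**Step B: reproduce the plan's figure.** The mediation section states none, so the sample-size inputs were checked against Table 5 (Section 11.2): 10 facilities per group, 60 patients each, ICC 0.10, alpha 0.05 (taken as two-sided).
- Design effect = 1 + (60 − 1) × 0.10 = 6.9; effective n per group = 600/6.9 = 86.96.
- Power = Φ(D / [σ√(2/86.96)] − 1.96).
- For D = 0.034 and σ = 0.08: standard error 0.0121, ratio 2.80, power Φ(0.84) = 80.0%.
- The other cells give 61.1%, 90.9% and 80.9%, against 61%, 91% and 81% stated. Table 5 reproduces.

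**Step C: run the three steps on simulated trials.** 20 facilities × 60 patients × 60 sessions, control rate 0.20, SD of patient proportions about 0.08, ICC about 0.10, 1,500 trials per scenario. Each step used a linear model with a facility random intercept and no covariates; the arm effect was tested on 18 df. Assumptions not in the documents: normal lowest SBP with session SD 20 mmHg, the distribution of highest SBP, and the correlation r between IDH and a downstream variable. The starting-SBP condition was not simulated. No simulated variable was a separate cause of IDH.

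Step 1 passed in 81.4% of trials at D = 0.034 and 95.9% at D = 0.043. With no true effect it passed in the beneficial direction in 2.4%. Given that step 1 passed:

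| Candidate mediator | Passes steps 2 and 3, D = 0.034 | D = 0.043 | Median share apparently mediated (D = 0.034) |
|---|---|---|---|
| Lowest SBP | 98.4% | 99.4% | 1.00 |
| SBP range, highest SBP unaffected by arm | 97.5% | 99.2% | 0.92 |
| SBP range, highest and lowest moving in parallel | 0.2% | 0.1% | 0.00 |
| Downstream of IDH, r = 0.2 | 26% | 35% | 0.03 |
| Downstream, r = 0.3 | 48% | 61% | 0.08 |
| Downstream, r = 0.5 | 77% | 88% | 0.23 |
| Downstream, r = 0.7 | 90% | 96% | 0.46 |
| Pure noise | 0% | 0% | 0.00 |

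For the downstream variables, step 3 is nearly automatic: the effect shrinks in 95-100% of trials and the mediator is significant in 100%. Step 2 is what limits them.

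**Step D: session-level logistic model.** With 5,000 simulated sessions, entering arm and lowest SBP gave complete separation and the fit stopped on a singular matrix.

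**The case against.** The strongest reply is that this is a supplementary analysis which the plan says is not causal, and that all three steps must be passed. Much of that stands.
- A reader might infer that the listed variables will all be reported as mediators by construction. The documents do not support this. Step 1 needs a significant effect, and step 2 is a real hurdle for consequences of IDH, as the 26-96% range shows. In the session-level logistic model, lowest SBP would produce a failed fit rather than a reported mediation.
- A reader might also infer that a circular result would displace modifiable mechanisms such as treatment time or ultrafiltration rate. It cannot do so in the models, because each mediator is tested on its own.
- Nor does the plan say that the mediation test itself will identify the pathways. In Section 11.4 that role is given to the changes in patient and practitioner behavior.
- Item (10) describes its readings as a measure of range. A range that does not track the nadir would show no mediation. But the item names the values themselves, and a range driven by the nadir behaves like the nadir.
- Symptoms are not only consequences here. Sections 2.1.4 and 2.2.1 want early symptom reporting to prompt action before IDH worsens, so striking symptoms out entirely would discard a hypothesized pathway. Item (9) likewise offers a pre-IDH version.
- Delivered treatment time and average session ultrafiltration rate need the same care. Both are whole-session values, and Section 2.1.3 notes that symptoms can shorten a session.

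None of this rescues lowest SBP, and the non-causal caveat does not turn a restatement of the outcome into information about mechanism.

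**Conclusion.** The point holds for lowest SBP without reservation: the definition and the mediator list use the same reading. Given a significant effect, it passes the remaining steps in 98-99% of simulated trials and appears to mediate about 100% of the effect in a linear model; at session level, a logistic model separates. For symptoms and recovery time, hospitalization and quality of life, the supported statement is that they can pass without being pathways. How often depends on correlations that the documents do not give. The percentages rest on the assumed SBP distribution, linear models without covariates and the stated r values; the circularity in item (10) rests on none of these. The primary analysis and the power in Table 5 are unaffected.

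**What to change.** In Section 11.4, for mediators of IDH:
- Delete lowest and highest SBP (session-level item 10).
- Keep SBP slope (item 9) only in the version truncated at IDH, and define a comparable window for sessions without IDH.
- State that every mediator must be measured before the session outcome. Use lagged or pre-IDH values for symptoms and recovery time, hospitalization, delivered treatment time and ultrafiltration rate. Where the outcome is a patient's proportion of unstable sessions, close the mediator window before the outcome window opens.
- Drop quality of life unless the survey precedes the sessions analysed.
- Reconcile the Aim 1 and Aim 2 lists, so that each states which direction is being tested and over what period.

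The cost is an edit to the plan before analysis and some programming of lagged variables from session records already being collected. No new data are needed, and the primary analysis does not change.
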